15.8.2 Clinical study registration

Takeda Pharmaceutical Company Limited will ensure timely publication of the information of a clinical study and registration of all clinical researches in patients under way all over the world, prior to study initiation, with ClinicalTrials.gov, JAPIC, and UMIN to comply with the applicable laws/regulations and guidelines. The city and country where a study is performed, and the subject recruitment status should be registered as well as the contact information of Takeda Pharmaceutical Company Limited to enable general access.

15.8.3 Clinical trial results disclosure

Takeda Pharmaceutical Company Limited will post the results of a clinical study on ClinicalTrials.gov, JAPIC, and UMIN as specified by the applicable laws and/or regulations irrespective of results.

15.8.4 Method of storage and destruction of material/information concerning clinical study

The director of the study site should appropriately retain the material/information related to this study for at least to the date passing 5 years from the date of reporting of the ending of the study from the investigator or to the date passing 3 years from the date of reporting of final publication of the study result, whichever date is later.

CONFIDENTIAL

15.9 Insurance and compensation for injury

The subjects participating in this study will be compensated for any injury resulting from participation in the study according to local regulations applicable to the study site. It should be noted that any treatment provided will be covered by health insurance, and no monetary compensation will be provided.

Appendix A Evaluation according to RECIST ver 1.1

Evaluation will be conducted according to RECIST ver 1.1 as follows.

1. Definition of measurable lesion

Lesion that fulfills any of the conditions below will be considered as a measurable lesion.

- (1) Lesions other than malignant lymph node (non-nodal lesion) that meet either of the below
 - 1) CT scan slice thickness no greater than 5 mm or MRI largest diameter at least 10 mm
 - 2) CT scan slice thickness greater than 5 mm or MRI largest diameter is 2 folds or more the slice thickness
- (2) Malignant lymph node CT scan slice thickness 5 mm or less and short diameter at least 15 mm
(Malignant lymph node with short diameter at least 10 mm and less than 15 mm will be a non-target lesion, lymph node with short diameter of less than 10 mm will not be considered as a lesion)

Any other lesion besides the above will be considered as non-measurable lesions.

Note that lesions below will be considered as non-measurable lesions irrespective of test method or size of lesion:

- Bone lesions
- Cystic lesions
- Tumour lesions situated in a previously irradiated area, or in an area subjected to other loco-regional therapy
- Leptomeningeal disease lesion
- Ascites, pleural effusion, pericardial effusion
- Lymphangitic involvement of skin or lung
- Abdominal masses/abdominal organomegaly identified by physical exam that is not measurable by reproducible imaging techniques

2. Baseline documentation of target lesions

From measurable lesions observed before initiation of protocol treatment, select 5 lesions highest in diameter (long diameter for non-nodal lesion and short diameter for malignant lymph node), 2 lesions at most for 1 organ and determine them as target lesions. Upon selection, organs with measurable lesions should be included evenly, and select in consideration of those that lend themselves to reproducible repeated measurements (lesions with large diameter but difficult to measure should be avoided).

For chosen target lesion, in order from head to tail, record site, lesion diameters (long diameter for non-nodal target lesions, short axis for nodal target lesion) and a sum of diameters (hereinafter referred to as SoD) of all target lesions should be recorded.

3. Baseline documentation of non-target lesions

Lesions not selected for target lesion should be recorded as present or absent non-target lesion irrespective of whether measurement is possible or not. Multiple non-target lesions in the same

CONFIDENTIAL

organ can be recorded as 1 lesion (e.g. multiple enlarged pelvic lymph nodes, multiple liver metastases)

4. Tumor response criteria

Evaluate target lesion and non-target lesion using the same method as at enrollment according to “9.2.10 Imaging test (thoracoabdominal-pelvic CT/MRI)“, and record diameter of target lesion, presence or absence of non-target lesion or onset of new lesion.

5. Response criteria of target lesion

• CR (Complete Response):

Disappearance of all non-nodal target lesions and all lymph node target lesions short axis <10mm If nodal target lesion is selected at baseline, response criteria may be CR even though SoD is not 0 mm.

• PR (Partial Response):

At least a 30% decrease in the SoD of target lesions, taking as reference the baseline SoD.

• PD (Progressive Disease):

Taking as reference the smallest sum on study (this includes the baseline sum if that is the smallest on study), at least a 20% increase in the SoD of target lesions, and the sum must also demonstrate an absolute increase of at least 5 mm.

• SD (Stable Disease):

Neither sufficient shrinkage to qualify for PR nor sufficient increase to qualify for PD, taking as reference the smallest SoD while on study.

• Not all Evaluated:

When test cannot be conducted for some reason, or cannot be determined as CR, PR, PD or SD.

$$\text{Reduction ratio of SoD} = \frac{\text{SoD before treatment} - \text{SoD at evaluation}}{\text{SoD before treatment}} \times 100\%$$

$$\text{Increase ratio of SoD} = \frac{\text{SoD at evaluation} - \text{Smallest SoD}}{\text{Smallest SoD}} \times 100\%$$

* Diameter of target lesion is recorded with actual measurements (e.g., even if under 5 mm) as much as possible, but when target lesion is determined as “too small to measure”, irrespective of CT slice thickness, if it is determined that tumor lesion no longer exists and the diameter will be recorded as 0 mm, whereas if it is determined to exist the diameter will be 5 mm.

- * If reduction ratio meets the PR criteria and increase ratio meets the PD criteria at the same time, criteria will be determined as PD.
- * If one lesion is divided during treatment, each diameter should be added to the SoD.
- * If multiple lesions agglutinate and the border cannot be distinguished, the diameter of the agglutinated lesion should be added to the SoD.
- * Whenever lesions are in contact, if the borders of the lesions are distinguishable, the diameter of each lesion should be added to the SoD.

6. Response criteria of non-target lesion

- CR (Complete Response):
Disappearance of all non-nodal non-target lesions and all lymph nodes short axis <10mm
- Non-CR/non-PD:
Persistence of one or more non-target lesion(s) including lymph nodes short axis \geq 10 mm and/or maintenance of tumor marker either of which the level is above the common normal limits.
- PD (Progressive Disease):
“Uequivocal progression” of existing non-target lesions (including recurrence).
When the patient has measurable lesion: In this setting, to achieve “unequivocal progression” on the basis of the non-target disease, there must be an overall level of substantial worsening in non-target disease such that, even in presence of SD or PR in target disease, the overall tumor burden has increased sufficiently to merit discontinuation of therapy. When response criteria for target lesion is SD or PR, an increase of non-target lesion that will overwhelm the tumor burden decrease will be determined as “unequivocal progression”, and if not it will be Non-CR/non-PD.
When the patient has only non-measurable lesion: a 20% increase diameter in a non-measurable lesion, an increase in tumor burden representing an additional 73% increase in ‘volume’ will be determined as “unequivocal progression”.
- Not all Evaluated:
When test cannot be conducted for some reason, or cannot be determined as CR, Non-CR/non-PD, or PD.

7. Appearance of new lesions

When a lesion that was not present at baseline has been observed after initiation of treatment, this will be determined as appearance of “new lesion”. However, “new lesion” should not be attributable to differences in scanning technique, change in imaging modality or findings thought to represent something other than tumor. For example, necrosis of a liver lesion may be

reported as a “new” cystic lesion, which it is not. A newly identified lesion in a location by test that was not mandatory at baseline (evaluation before enrollment) is considered a new lesion. If a lesion disappears and reappears later, measurement will be continued. However, the response at the time of reappearance of the lesion will be different depending on other lesions. If lesion has reappeared after CR, it will be determined as PD at the time of reappearance. On the other hand, if it was PR or SD, when the once disappeared lesion reappears, in order to calculate the response, the diameter of the lesion will be added to the rest of the lesions. Thus, when there are a number of lesions still existing, if one lesion apparently “disappears” and reappears later, from that alone, it will not be determined as PD but if the SoD of all the lesions meet the PD criteria, it will be determined as PD. The reason for this is that there is an understanding that most of the lesions do not truly “disappear” and yet it cannot be extracted due to the limit to resolution of imaging modality.

If there is a possibility of new lesion but cannot be confirmed, it should not be determined as a new lesion but re-examination by imaging test should be conducted after clinically appropriate interval. If new lesion is confirmed by imaging test re-examination, the date of the imaging test that confirmed the new lesion will be the time point for appearance of new lesion.

8. Overall Response

Overall Response will be determined with combination of target lesion response, non-target lesion response, appearance of new lesion according to Tables A.1 and A.2 below.

Table A.1 Overall response at each time point: When patient has target lesion (with or without non-target lesion)

Target lesion	Non-target lesion	New lesion	Overall response
CR	CR	Absent	CR
CR	Non-CR/non-PD	Absent	PR
CR	Not determined	Absent	PR
PR	Non-PD or defect in evaluation	Absent	PR
SD	Non-PD or defect in evaluation	Absent	SD
Defect in evaluation	Non-PD	Absent	NE
PD	Any	Present or absent	PD
Any	PD	Present or absent	PD
Any	Any	Yes	PD

9. Best Overall Response

Response will be more favorable in the following order: CR>PR>SD>PD>NE. The most favorable overall response through the entire course will be the best overall response.

When response could not be determined by imaging due to an obvious aggression of disease or death before the first response determination, it will be determined as PD. When response could not be determined by imaging due to discontinuation from toxicity or rejection by subject before the first response determination, it will be determined as NE.

Appendix B

Responsibilities of the investigator

1. To appropriately conduct the study in accordance with the protocol, Ethical Guideline for Clinical Research and the ICH-GCP considering the human rights, safety, and wellbeing of human subjects.
2. When assigning a part of important duties related to this study to subinvestigators or study collaborators, prepare a list of subinvestigators or study collaborators, which will be submitted to the director of study site as necessary.
3. To prepare the informed consent form and revise it as necessary.
4. To check the contents of the study contract.
5. To provide sufficient information on the protocol, drug and duties of each personnel to subinvestigators and study collaborators, and give guidance and supervision.
6. To select subjects who satisfy the protocol, give explanation using written information, and obtain consent in writing.
7. To be responsible for all medical judgments related to the study.
8. Corresponding to request from the director of the study site, report the latest progress status at least once a year to the director of the study site.
9. To request COI committee of each study site to review and approve that there is no COI issues in conducting this study.
10. To ensure together with the director of study site that sufficient medical care is provided to subjects for all study-related clinically problematic adverse events throughout the period of subject's study participation and thereafter.
11. When a subject is treated at another medical institution or department, inform a physician of the medical institution or department in writing of the subject's study participation and study completion/discontinuation after obtaining the subject's consent, and prepare the record.
12. When emergency report of serious adverse events, etc. is required, immediately report it in writing to the director of the study site and the sponsor.
13. To prepare accurate and complete CRF and submit it to the sponsor with an electronic signature.
14. To inspect and check the contents of CRF prepared by subinvestigators, or transcribed by study collaborators from the source data, and submit it to the sponsor with an electronic signature.
15. To discuss a revision of the protocol, etc., when proposed by the sponsor.
16. To report the study completion in writing to the director of study site.

CONFIDENTIAL

7.2.1 Eligibility and analysis set.....	10
7.2.2 Analysis of demographic and other baseline characteristics.....	11
7.2.3 Medication status.....	11
7.2.4 Efficacy analysis.....	13
7.2.5 Safety analysis.....	19
7.2.6 Other safety analysis items	20
7.2.7 Table listing	21
7.3 Criteria for interim analysis and premature discontinuation	24
7.4 Sensitivity analysis.....	24
8. References	25

[figure not shown]
1. History of preparation and revision

Version	Date of approval	Author	Reason for revision
1.0	June 3, 2016	PPD	Not applicable, because it is the first version
2.0	February 28, 2017	PPD	(1) Addition of definition of protocol treatment and acceptable range (2) Addition of analysis plan for phase II part
3.0	December 28, 2017	PPD	(1) Addition of analysis items associated with the protocol revision (ver. 2.0) (2) 7.2.3 Completion of administration (3) 7.2.3.3 Dose reduction status
4.0	July 10, 2018	PPD	(1) 3. Time Period for Analysis is clarified. (2) MedDRA version is stated. (3) Addition of following analysis items: 7.2.3.2 7.2.3.3 7.2.4.3 1) and 2) 7.2.4.4 7.2.6.3 7.2.6.4 7.2.6.5

2. Analysis Plan Objectives

This analysis plan specifies how the initial and final analyses of the clinical study are planned to be conducted in accordance with the “Clinical Study Protocol of A phase I/II study for the safety and efficacy of Panitumumab in combination with TAS-102 for patients with RAS wild-type metastatic colorectal cancer refractory to standard chemotherapy” (hereinafter, protocol).

The study design is shown below.

3. Time period for Analysis

Phase I part: Analysis will be performed after completion of enrollment for phase I, after completion of the Dose Limiting Toxicity (DLT) evaluation period for all enrolled subjects, and after completion of DLT evaluation. A statistical analysis plan for conference presentation will be prepared separately, and analysis will be performed accordingly. Similarly, analysis will be performed again at completion of the period for all observations (final analysis).

Phase II part: Analysis will be performed after completion of enrollment for phase II part and when evaluation has been performed in all the enrolled subjects at 6 months after the start of protocol treatment (initial analysis) and at completion of period for all observations (final analysis).

Protocol treatment

With protocol treatment, in principle, combination therapy with panitumumab and TAS-102 will be conducted, and even if any of the criteria for suspension or discontinuation of either drug is met, treatment with other drugs will be continued unless any of the criteria for discontinuation of protocol

treatment is met (Section 8.7 of protocol). Protocol treatment in principle will be initiated within 14 days of entry.

4. Analysis data set

4.1 Handling of cases/data

(1) Handling of laboratory values/subjective and objective findings of adverse events

Adverse events recorded on the adverse event form will be coded using Medical Dictionary for Regulatory Activities (MedDRA) (ver.21.0) and summarized by system organ class (SOC) and preferred terms (PTs). Skin disorders will be regarded as events classified into “Skin and subcutaneous tissue disorders” of SOC or “Paronychia” by PT. The PTs classified as skin toxicity (Rash acneiform, Paronychia, Dry skin, Pruritus) are defined in Table 4.1.

Table 4.1 Events classified as skin toxicity

Rash acneiform	Acne, Dermatitis acneiform, Folliculitis, Rash, Dermatitis, Drug eruption, Rash pruritic, Eczema, Skin disorder, Rash generalized, Seborrhoeic dermatitis
Paronychia	Paronychia, Nail avulsion, Onychoclasia, Onychomadesis, Nail disorder, Ingrowing nail, Excessive granulation tissue, Pyogenic granuloma
Dry skin	Dry skin, Skin fissures, Xeroderma, Skin exfoliation, Skin chapped, Eczema asteatotic, Hyperkeratosis
Pruritus	Pruritus, General pruritus

(2) Handling of adverse event grade

If an AE is assessed multiple times in the same subject, the highest grade among all AE assessments shall be reported as the worst grade of the AE.

(3) Handling of missing/ejected data

Missing data will not be complemented unless the details of individual analysis items are specified. When rejecting data, the corresponding data will be indicated and the reason for rejection clarified in a table. However, handling of patients with no occurrence of events related to Progression-Free Survival (PFS), Overall Survival (OS), or Time to Treatment Failure (TTF) will be described in each section.

(4) Protocol treatment and acceptable range for tests

Performed items	Protocol specification	Allowance range
Protocol treatment	From the date of treatment of the previous course (Day 1) to after 4 weeks (Day 29)	Scheduled day \pm 3 days

4.2 Number of significant figures in analysis results

Percentages (%) expressing frequency distribution will be rounded to one decimal place unless the details of individual analysis items are specified.

Among summary statistics (number of cases, the mean, standard deviation, minimum, maximum, and inclusive quartiles), the mean, standard deviation, and quartiles will be rounded to one decimal place lower than the original data.

P-values will be indicated to 4 decimal places rounded from the 5th decimal. However, a p-value less than 0.0001 will be expressed as “p < 0.0001.” Hazard ratios and their 95% confidence intervals will be indicated to 2 decimal places rounded from the 3rd decimal.

5. Software used for analysis

The statistical software used for analysis will be CCI

6. Statistical analysis of the phase I part of the study

6.1 Analysis set

Two analysis sets will be created for the phase I part of the study: “set of enrolled subjects who received at least one dose of protocol treatment and satisfied all of the enrollment criteria” and the “DLT evaluation set.” The DLT evaluation set will be based on the following definition from the protocol, Section 8.9.2:

Subjects enrolled in the phase I part of the study will be included in the DLT evaluation set. Subjects will be excluded from the DLT evaluation if at least the designated dose of protocol treatment is not administered by the end of Course 1 (except when the protocol treatment is discontinued due to DLT), if there are major protocol deviations such as the use of contraindicated drugs, or if the subject is determined to be unsuitable for the DLT evaluation. The designated dose is 75% (15 doses) of the total number of doses (20 doses) of panitumumab (2 doses of 6 mg/kg) and TAS-102 (2 doses daily of 35 mg/m²) on Days 1-5 and Days 8-12.

6.2 Analysis of demographic and other baseline characteristics

The following analyses will be conducted in the “set of enrolled subjects who received at least one dose of protocol treatment and satisfied all of the enrollment criteria” and the “DLT evaluation set.”

(1) Discrete data:

A frequency distribution for the discrete data will be computed indicating the percentage (%) with the analysis set as a denominator. Aggregation items are as follows:

- Age (≥ 20 to < 30 years, ≥ 30 to < 40 years, ≥ 40 to < 50 years, ≥ 50 to < 60 years, ≥ 60 to < 70 years, ≥ 70 to < 75 years; ≥ 20 to < 65 years, ≥ 65 to < 75 years), sex, information on primary organ tumor (solitary, multiple), primary tumor location [colon (cecum, ascending colon, transverse colon, descending colon, sigmoid colon), rectum (rectosigmoid, rectum)], [right side, left side], information on metastasis (number of organs with metastasis) (0, 1, ≥ 2), organs with metastasis (liver, lung, peritoneum, lymph node, bone, adrenal gland, skin, and others), ECOG Performance status (P.S.) [before treatment on Day 1 of Course 1 (0, 1)], resection of primary tumor (yes, no), adjuvant chemotherapy (yes, no), number of previous treatments (1, 2, 3), complications (absence, presence)

Determination of primary tumor location:

Right side: in the case of solitary or multiple lesions in the cecum, ascending colon, and transverse colon

Left side: in the case of solitary or multiple lesions in the descending colon, sigmoid colon, rectosigmoid, and rectum

(2) Continuous data:

Summary statistics (number of cases, mean, standard deviation, minimum, maximum, and

inclusive quartiles) will be calculated for continuous data.

- Age (years), height (cm), body weight (kg) (at enrollment), BMI (kg/m^2) (at enrollment), period from the start date of first-line treatment to the date of enrollment (months) (One month is considered as 28 days in calculations).

6.3 Safety analysis

6.3.1 Incidence of DLT events with panitumumab + TAS-102 combination therapy

In accordance with the protocol, Section 8.9.3., the number of cases determined as DLTs among subjects in the DLT evaluation set will be shown and the percentage (%) will be indicated with the total number of cases in the DLT evaluation set as a denominator.

6.3.2 Listing of DLT events

A table listing events determined as DLTs in the DLT evaluation set will be prepared.

Display items:

Subject No., sex, age (years), BMI (kg/m^2) (at enrollment), protocol treatment initiation date, DLT event name (event name recorded by physician, Lowest Level Terms [LLT] code, LLT (English, Japanese), PT code, PT (English, Japanese), SOC code, SOC (English, Japanese), date of onset, severity, causal relationship of adverse event with protocol treatment, causal relationship with panitumumab, seriousness, discontinuation of protocol treatment, outcome, date of resolution

6.3.3 Frequency tabulation of adverse events

The following analyses regarding treatment-emergent adverse events (TEAEs) will be performed on the “set of enrolled subjects who received at least one dose of protocol treatment and satisfied all of the enrollment criteria” and the “DLT evaluation set.”

TEAEs are adverse events that develop after initiation of protocol treatment.

Skin toxicity are events meeting the definitions of TEAEs in [Table 4.1](#).

TEAEs will be coded using MedDRA and summarized by SOC and PTs.

A subject with multiple events in the same SOC will be counted once for that SOC. A subject with multiple events with the same PT will be counted once for that PT.

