8.7 Criteria for discontinuation of protocol treatment for each subject

The number of doses is not specified. However, protocol treatment should be discontinued when any of the criteria for discontinuation of protocol treatment listed below is met. The date of discontinuation of protocol treatment is defined as the date when the investigator or the subinvestigator decides on discontinuation of protocol treatment. The investigator or the subinvestigator should record the main reason for discontinuation of protocol treatment in the case report form (hereinafter referred to as CRF) according to the classification described below. For subjects discontinuing before enrollment, see 9.3 Records of subjects who discontinued before enrollment.

1. Lack of efficacy (exacerbation)

When PD is evident in the clinical or imaging evaluation

2. Adverse event

Discontinuation of treatment due to an adverse event in the opinion of the investigator or the subinvestigator, or according to the protocol treatment discontinuation criteria. However, death during protocol treatment will be classified in “4. Death during protocol treatment” and not in this item.

Protocol treatment is postponed due to adverse event for 58 days or more after the day of starting the last course. However, postponement due to holidays is allowed.

3. Voluntary discontinuation

A subject wishes to discontinue study participation. The reason for discontinuation should be recorded in CRF when it is clarified.

CONFIDENTIAL

Note: Attempts should be made as best as possible to clarify the reason for voluntary discontinuation. (Discontinuation due to adverse event or lack of efficacy should not be classified as “voluntary discontinuation”).

4. Death during protocol treatment

Death before discontinuation of protocol treatment is decided. Date of death, reason of death (protocol treatment related, primary disease, others) should be described in the CRF.

5. Significant deviation from the protocol

When study continuation may cause intolerable risk to the health of a subject because the subject was found not to satisfy the inclusion criteria specified in the protocol after enrollment or the protocol has not been observed.

6. Lost to follow-up

When subject fails to make visits and cannot be contacted. The attempts that were made to contact the subject should be recorded in the source documents.

7. Discontinuation of the entire study

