7.1 Analysis set

In the phase II part of the study, statistical analysis will be performed on a “full analysis set” and “safety analysis set.” The “full analysis set” will be the main efficacy analysis set, and is defined as “subjects enrolled in phase I and II who received at least one dose of protocol treatment (RD) and satisfied all of the enrollment criteria.” RD is the recommended dose that is confirmed in the phase I part. The “safety analysis set” is defined as “subjects enrolled in phase I and II who received at least one dose of either panitumumab or TAS-102.” Additionally, the set of all subjects who are enrolled in this study is defined as “all enrolled subjects.”

The statistics representative and analysis personnel should finalize a statistical analysis plan before data fixation based on confirmation of the definition of analysis sets and appropriateness of analytical handling rules of the subject data in the analysis sets, and additional handling rules for the issues that are not determined at planning before data fixation.

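### The phase I adverse event tables have no all-treated set: a treated subject who is ineligible and also outside the DLT evaluation set appears in no SAP section 6 table

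*SAP*

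**What the plan says.** SAP v4.0 section 6.1 states: "Two analysis sets will be created for the phase I part of the study". Protocol 13.2.1 says the same.

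- **First set:** the "set of enrolled subjects who received at least one dose of protocol treatment and satisfied all of the enrollment criteria".
- **Second set, the DLT evaluation set:** it starts wide, since "Subjects enrolled in the phase I part of the study will be included in the DLT evaluation set". A subject is then taken out on any of three grounds. The first is dosing: "if at least the designated dose of protocol treatment is not administered by the end of Course 1" (the designated dose being 75% of the planned doses, with an exception for treatment stopped because of DLT). The second is conduct: "if there are major protocol deviations such as the use of contraindicated drugs". The third comes without criteria: "or if the subject is determined to be unsuitable for the DLT evaluation".

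Sections 6.3.1 and 6.3.2 (DLT incidence and listing) use the DLT set. The baseline tables in 6.2, the TEAE tables 6.3.3.1 to 6.3.3.20 and their repeat for skin toxicity use both sets. Section 6 defines no other set.

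SAP 7.1 defines a safety analysis set for the phase II part: phase I and phase II subjects who received "at least one dose of either panitumumab or TAS-102". It carries no eligibility condition. It feeds the pooled tables in 7.2.5 and the TEAE listing in 7.2.7.8, which shows each subject's enrollment phase.

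**The concern.** Phase I is there to judge tolerability, and the toxicity of a treated subject is informative about the regimen whether or not an enrollment criterion was missed. An eligibility condition on a safety table can therefore remove relevant events.

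Here the first set applies that condition, and the second can remove the same subject for other reasons. The two removals can share one cause. Protocol 8.7 places the case where "the subject was found not to satisfy the inclusion criteria specified in the protocol after enrollment" under significant deviations and, where continuing may cause intolerable risk, makes it a reason to stop treatment. Stopping in Course 1 for that reason can leave the subject below the designated dose, and the exception in SAP 6.1 covers only stops due to DLT.

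The pooled section 7 tables do not fill the place of a phase I summary. They have no split by phase. Under SAP section 3 they also come later: the phase I analysis follows DLT evaluation, whereas the phase II analysis waits until enrollment is complete and all subjects have been evaluated at 6 months.

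**Working it through.** **Phase I size.** Protocol 6.1 gives two cohorts of 3, so 3 + 3 = 6 per dose level. Repeating at a reduced dose gives 2 × 6 = 12, which reproduces the 6 to 12 in Protocol 6.2.2.2. Adding the 46 phase II subjects gives 6 + 46 = 52 at the recommended dose and 12 + 46 = 58, the stated maximum.

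**Where a treated, ineligible phase I subject appears.**

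| Situation in Course 1 | First set | DLT set | Section 6 TEAE tables | Section 7 safety set and TEAE listing |
|---|---|---|---|---|
| Designated dose reached, no other exclusion | Out | In | Shown in the DLT-set version | Shown |
| Stopped for DLT, no other exclusion | Out | In | Shown in the DLT-set version | Shown |
| Below designated dose for another reason | Out | Out | **Not shown** | Shown |
| Counted as a major deviation, or judged unsuitable | Out | Out | **Not shown** | Shown |

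**Weight of one subject.** 1/6 = 16.7%; 1/12 = 8.3%. In the pooled safety set, 1/52 = 1.9% and 1/58 = 1.7%.

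**Effect on a reported rate.** The documents give no results, so these counts are assumed. The interval is the Agresti-Coull 95% interval that the SAP specifies: with z = 1.96, n' = n + z², p' = (x + z²/2)/n', limits p' ± z√(p'(1 − p')/n'), cut at 0.

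- One Grade 3 or higher event, in the lost subject: all treated 1/6 = 16.7% (1.1% to 58.2%); as tabulated 0/5 = 0% (0% to 48.9%).
- Three subjects with events, one of them lost: 3/6 = 50.0% becomes 2/5 = 40.0%. If the lost subject had no event, it becomes 3/5 = 60.0%.
- Twelve subjects, one event, in the lost subject: 1/12 = 8.3% becomes 0/11 = 0%.
- Protocol 8.10 allows a subject excluded from the DLT evaluation to be replaced. If the replacement is eligible and has no event, the table shows 0/6 against 1/7 = 14.3% of those treated. Replacement restores the denominator but not the event.

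**How often.** Let p be the chance that a treated subject is later found ineligible, taken as independent between subjects. The documents do not give p. Protocol 6.2.2.2 allows about 10% for ineligible and discontinued subjects together, so 10% is at the high end; 5% to 10% is used here.

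- First set loses at least one of 6: 1 − (1 − p)⁶. At 5%, 1 − 0.95⁶ = 0.265 (26%). At 10%, 1 − 0.90⁶ = 0.469 (47%).
- At least one of 6 absent from both sets: 1 − (1 − pq)⁶, where q is the share of ineligible subjects also excluded from the DLT set. The documents give no q. If q is 20% to 50%, the result runs from 1 − (1 − 0.05 × 0.2)⁶ = 0.059 (6%) to 1 − (1 − 0.10 × 0.5)⁶ = 0.265 (26%).

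**The case against.** The case on the other side is substantial, and most of it stands as a limit on the point.

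- **Ineligibility alone is not enough.** A reader might infer that any ineligible subject drops out of all phase I safety tables. The DLT set has no eligibility condition, so an adequately dosed ineligible subject stays in the DLT-set version of every 6.3.3 table. A subject stopped for DLT is also kept.
- **The deviation route is open but not stated.** The only example of a major deviation in SAP 6.1 is contraindicated drugs, and Protocol 8.10 concerns deviations that affect the DLT evaluation. Protocol 8.7 is about stopping treatment. Nothing says that ineligibility by itself removes a subject from the DLT set.
- **The data are not lost.** The section 7 safety set, its tables and the listings by enrollment phase keep every treated subject, and SAP 7.2.7.2 lists exclusions with reasons. With 6 to 12 subjects, a reader could rebuild the phase I counts from the listing.
- **The dose decision does not hang on these tables.** A reader might infer that the DLT result or the move to phase II is biased. The DLT result comes from 6.3.1 and 6.3.2 on its own set. Under Protocol 6.1 the move also draws on the phase I safety data and the data monitoring committee's opinion, and Protocol 10.2.2 requires serious events to be reported whatever the subject's eligibility.
- **Eligibility errors should be few.** Protocol 7.0 requires all criteria to be confirmed before enrollment, and the registration system checks them.

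None of this supplies a phase I summary of all treated subjects. A listing is not a rate with an interval, and the pooled tables dilute one subject from 16.7% to under 2%.

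**Conclusion.** The gap is real but narrow. A treated subject found ineligible is always missing from the first phase I set, and is missing from every section 6 table only if also excluded from the DLT evaluation set. The consequence is an incomplete phase I summary; no events are lost from the trial's safety reporting and the DLT result does not change.

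When it happens, one subject is 16.7% of a 6-subject part or 8.3% of 12, enough to turn 1/6 into 0/5. The 26% to 47% applies to the first set losing at least one of 6 subjects and rests on the assumed 5% to 10% ineligibility. It should not be read as the chance of absence from both sets, which is lower by an amount the documents do not allow one to fix. This is a worthwhile tidying of the plan, not a threat to its conclusions.

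**What to change.** In SAP 6.1, add a phase I safety set: all phase I subjects who received at least one dose of either drug, which is the 7.1 definition restricted to phase I. In 6.3.3, run 6.3.3.1 to 6.3.3.20 and the skin toxicity repeat on it. Add the 6.2 baseline table for the same set, so that the safety rates and the description of the subjects refer to the same people. Keep the DLT evaluation set for 6.3.1 and 6.3.2.

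No new data are needed, and SAP section 3 already repeats the phase I analysis at the end of observation. The cost is one more set of tables. Changing Protocol 13.2.1 now might count as a change in safety evaluation method under Protocol 6.4 and so need an amendment. Making the addition in the SAP and aligning 13.2.1 at the next amendment avoids that.
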